3.1 Independent ethics committee

It is the responsibility of the investigator to ensure approval of the study protocol, possible amendments and the written patient information and informed consent form from the Independent ethics committee (IEC) before commencing the study. The investigator should file all correspondence with the IEC as applicable. Copies of IEC correspondence and approvals should be forwarded to the Contract research organization (CRO).

3.2 Ethical consideration of the study

This study will be conducted in compliance with this protocol, the International council for harmonisation Good clinical practice (ICH GCP) (2), European regulation 536/2014 (3) for clinical studies, other applicable regulatory requirements, and in accordance with the ethical principles that have their origin in the 2013 version of the Declaration of Helsinki) (4).

3.3 Patient information and consent

It is the responsibility of the investigator or designee to give each patient (or the patient's acceptable representative) prior to any study-related activities, full and adequate verbal and

Sobi

Eftrenonacog alfa/Alprolix® - Efmorocog alfa/Elocta®

Clinical Study No: Sobi.HAEM89-007

written information regarding the objective and procedures of the study and the possible risks involved. The patients must be informed about their right to withdraw from the study at any time.

The written patient information and/or informed consent/assent form must not be changed without prior discussion with Swedish Orphan Biovitrum AB (publ) (Sobi). Before any revisions are implemented, the revised written patient information and/or informed consent form must be approved by the IEC.

It is the responsibility of the investigator or designee to obtain signed informed consent (or witnessed verbal consent according to applicable regulations) from all patients prior to any study-related activities. The patients should receive a copy of the written information, the signed informed consent form and assent form for patients not being able to provide full consent (i.e. minors). Patients who become adults during the study duration will be re-consented as applicable in accordance with local regulations.

For patients willing to participate in the florio® HAEMO sub-study (see section 6.5.11), a separate consent will be obtained.

4 Introduction

4.1 Background

Haemophilia is a rare genetic disorder characterized by a deficiency in coagulation factor VIII (FVIII; haemophilia A) or factor IX (FIX; haemophilia B) causing impaired haemostasis and prolonged bleeding episodes. Severe haemophilia, defined as <1% of normal Factor VIII/FIX activity in haemophilia A and haemophilia B respectively, occurs in approximately 45% of haemophilia A and approximately 35% of haemophilia B patients, and results in frequent and spontaneous bleeds into muscles and joints, commonly the elbows, knees, and ankles (5, 6, 7). Bleeding into joints can cause acute pain and swelling and can result in reduced joint range of motion (ROM), long-term cartilage damage and haemophilic arthropathy (5). As a result of bleeding episodes and resulting progressive joint damage, haemophilia patients experience decreased physical functioning, pain, and poor health-related quality of life (HRQoL) (8).

The cornerstone of haemophilia treatment in patients with haemophilia A and B is FVIII or FIX prophylaxis, respectively, to prevent and control bleeding episodes and, consequently, prevent or slow down the development of arthropathy. In fact, joint damage and progressive chronic arthropathy are the hallmarks of haemophilia because a single or few repeated joint bleeds can lead to structural joint damage due to synovial inflammation caused by haemosiderin deposition (9). Synovial iron deposition and inflammatory cell proliferation provokes degeneration of joint surfaces and eventually loss of normal joint function (9, 10) and may lead to disabling arthropathy. In addition to its efficacy for arthropathy prevention, FVIII or FIX prophylaxis has been associated with improvements in HRQoL and opportunities for a more physically active life (11, 12).

Sobi

Eftrenonacog alfa/Alprolix® - Efmoroctocog alfa/Elocta®

Clinical Study No: Sobi.HAEM89-007

Extended half-life products used for replacement factor therapy have been developed utilizing Fc or albumin fusion technology, or pegylation, to prolong their half-life (13). Efmoroctocog alfa [a recombinant FVIII Fc fusion protein, Elocta®] (rFVIIIFc) and Eftrenonacog alfa [a recombinant FIX Fc fusion protein, Alprolix®] (rFIXFc) are recombinant coagulation factor concentrates with extended half-life. In contrast to standard half-life factor replacement products, the addition of the Fc region of human immunoglobulin G1 (IgG1) to the recombinant factor allows rFVIIIFc and rFIXFc to bypass lysosomal degradation and remain circulating in the bloodstream longer than standard half-life factor replacement products, thus prolonging the plasma terminal half-life. rFVIIIFc first received market authorization in June 2014 in the US, for the treatment of haemophilia A. Thereafter, in November 2015, it received market authorization in the European Union (EU) under the tradename Elocta®. rFIXFc first received market authorization in the US March 2014 and then in Europe in May 2016 for the treatment of haemophilia B under the tradename Alprolix®.

Despite the use of prophylaxis many patients still experience joint bleeds which may lead to joint deterioration over time (14, 15). Furthermore, not all bleeds may be clinically evident, as there are indications of subclinical bleeds in patients receiving treatment for their haemophilia (16). It is therefore important to gather additional information on the joint health of haemophilia patients using currently available examination methods.

Thorough examination of the joints and follow-up of patients is a crucial part of patient management and helps to identify when there is a need to adjust the treatment regimen. There are currently several examination methods to identify joint damage early on, including clinical joint examination and different imaging techniques. The functional Hemophilia Joint Health Score (HJHS) (17, 18, 19) for clinical joint assessment and more recently the Haemophilia Early Arthropathy Detection with UltraSound (HEAD-US) protocol for joint imaging are two established examinations.

The HEAD-US protocol has been developed for non-radiologists to assess synovial hypertrophy and cartilage defects using point-of-care ultrasound (US) examination, enabling direct assessment of joint health in conjunction with medical history and physical examination (20). The HEAD-US scoring method is based on an additive scale with assessment of ankles, knees and elbows. It includes indicators of disease activity (synovitis; hypertrophic synovium) and structural osteochondral damage (articular cartilage and subchondral bone).

Strengthening muscles can help improve joint health by reducing impacts on joints, and participation in sporting activities may help individuals compensate for motor skill deficits that arise because of complications of haemophilia, such as arthropathy (21). Among adults with haemophilia, regular physical activity helps prevent obesity and other chronic conditions; in children and adolescents with haemophilia, physical exercise supports joint, bone, and muscle health; weight control; and anxiety reduction (22).

However, patients may limit their physical activities due to fear of bleeding if they are unaware of their current FVIII or FIX level. Patient apps and wearables are now available which allow patients to view their estimated FVIII or FIX levels, and capture health-related data (such as bleeding episodes, pain, well-being, physical activity levels etc.).

Confidential

Page 14 of 56

Sobi

Eftrenonacog alfa/Alprolix® - Efmorocog alfa/Elocta®

Clinical Study No: Sobi.HAEM89-007

These data can be shared with the treating physician supporting the planning to individualize the patient's factor treatment based on current lifestyle, health status and physical activity levels.

florio HAEMO, a CE marked medical device used as part of routine clinical practice, consists of the florio HAEMO app (for patients with haemophilia and/or their caregivers) and the florio HAEMO dashboard (for healthcare professionals).

Synovitis is currently considered a marker of haemophilia activity and can be unnoticed on physical examination, especially in patients on prophylaxis. Performing point-of-care US examination is considered as the most practical option for regular monitoring of joints to detect soft tissue and osteochondral changes, and physical examination provide complementary information on the joint disease.

Favourable joint outcomes are expected with modern haemophilia A and haemophilia B management. However, evaluation of long-term treatment outcomes is hampered by the delay between bleeding episodes during childhood and resulting joint outcomes in adulthood. Future research with combined US and/or Magnetic resonance imaging (MRI) is needed to better understand joint outcomes. Ultrasound paired with physical examination increases the sensitivity for detection of joint damage (23). Accordingly, the expected joint health outcomes, based on HEAD-US scoring, in patients receiving adequate prophylactic treatment is at least the maintenance of a stable joint status or the improvement in reversible lesions for the patients with already established joint damage.

4.2 Study rationale

The efficacy and safety of rFVIIIFc and rFIXFc have been established in clinical trials as required for regulatory approvals. In addition, several completed and ongoing non-interventional studies describe the effectiveness and usage of rFVIIIFc and rFIXFc in the real-world setting (24, 25). However, there are still limited real-world data on joint health outcomes, assessed with objective measures, in patients receiving rFVIIIFc or rFIXFc prophylaxis.

The main purpose of this study is to prospectively describe the joint health over an 18-month period of prophylactic treatment with rFVIIIFc or rFIXFc in patients with haemophilia A or haemophilia B in a real-world setting in Europe. This is a low-interventional, multicentre study using point-of-care US examination for regular monitoring of soft tissue and osteochondral changes in the joints, as well as physical examination as a complementary assessment of joint disease.

Data output from florio HAEMO, and patient feedback via a patient questionnaire on physical activity levels and sense of protection while using florio HAEMO, will be analyzed as exploratory objectives in a sub-study. This sub-study will explore possible correlations between the levels of physical activity, the estimated FVIII/FIX levels and bleeding occurrence.

Sobi

Eftrenonacog alfa/Alprolix® - Efmorocog alfa/Elocta®

Clinical Study No: Sobi.HAEM89-007

4.3 Potential risks and benefits

This is a low-interventional study. While joint assessments with HEAD-US and HJHS may be part of the patient's usual routine clinical care, the study specific requirement to complete these assessments according to the study's schedule of events is considered a low intervention. The completion of Patient-reported outcomes (PROs) is also considered a low intervention. These interventions are not assessed to pose more than minimal risk to the patients.

rFVIIIFc and rFIXFc have marketing authorization and will be used per approved indication. They will be prescribed independently from the decision to enrol a patient in the study, and choice of treatment is hence not dictated by the study protocol.

Participation is not expected to have any particular benefit for the enrolled patients, other than a potentially more intensive follow-up by their physician. The results from the study may help in improving the knowledge of joint disease and US assessment in patients with haemophilia, and potentially in improving the management of haemophilic arthropathy in the future.

5 Study objectives and endpoints

5.1 Primary objective

To evaluate the overall joint status as detected by ultrasound in haemophilia A and B patients treated with rFVIIIFc or rFIXFc prophylaxis over the 18-month study period.

5.1.1 Primary endpoint

Change from baseline in total HEAD-US score up to month 18 (EOS).

5.2 Secondary objectives

- To evaluate the joint status as detected by ultrasound in the HEAD-US specific items of hypertrophic synovium, cartilage and bone damage in haemophilia A and B patients treated with rFVIIIFc or rFIXFc prophylaxis over the 18-month study period
- To evaluate the clinical joint status as detected by HJHS in haemophilia A and B patients treated with rFVIIIFc or rFIXFc prophylaxis over the 18-month study period
- To evaluate the presence, resolution, recurrence and new development of target joints in haemophilia A and B patients treated with rFVIIIFc or rFIXFc prophylaxis over 18 months
- To describe the bleeding episodes in haemophilia A and B patients treated with rFVIIIFc or rFIXFc prophylaxis over the 18-month study period
- To evaluate the QoL in haemophilia A and B patients treated with rFVIIIFc or rFIXFc prophylaxis over the 18-month study period

5.2.1 Secondary endpoints supporting the secondary objective(s)

- Change from baseline in HEAD-US score for hypertrophic synovium at 6, 12 and 18 months
- Change from baseline in HEAD-US score for cartilage at 6, 12 and 18 months
- Change from baseline in HEAD-US score for bone at 6, 12 and 18 months
- Change from baseline in total HJHS at month 18 (EOS)
- Number and location of target joints at baseline, 6, 12 and 18 months
- Total Annualized bleeding rate (ABR), joint ABR, target joint ABR, traumatic/spontaneous ABR
- Patient-Reported Outcomes Measurement Information System (PROMIS) physical function/activity scores at baseline and 18 months
- PROMIS pain intensity and interference scores at baseline and 18 months
- International Physical Activity Questionnaire - Short Form (IPAQ-SF) scores at baseline and 18 months

5.3 Exploratory objectives – florio HAEMO sub-study

- Impact of florio HAEMO on patients' sense of protection and their physical activity level in haemophilia A and B patients treated with rFVIIIFc or rFIXFc prophylaxis
- Explore adherence to prescribed treatment regimen in haemophilia A and B patients treated with rFVIIIFc or rFIXFc prophylaxis
- Explore relationship between estimated FVIII and FIX levels and physical activity in haemophilia A and B patients treated with rFVIIIFc or rFIXFc prophylaxis
- Explore timing of bleeding episodes in relation to estimated FVIII and FIX levels and physical activity in haemophilia A and B patients treated with rFVIIIFc or rFIXFc prophylaxis
- Explore the use of florio HAEMO to characterise pain and well-being in haemophilia A and B patients treated with rFVIIIFc or rFIXFc prophylaxis

5.3.1 Exploratory endpoints

- Results from questionnaire on impact of florio HAEMO tools on patients' sense of protection and their physical activity level
- florio HAEMO captured treatment adherence scores
- florio HAEMO captured estimated FVIII and FIX levels
- florio HAEMO captured physical activity type, duration and intensity
- florio HAEMO captured bleed data (timing, location, cause, treated/untreated)
- florio HAEMO captured FVIII/FIX administration data (time, dose)
- florio HAEMO captured pain data (time, location, cause, intensity)
- florio HAEMO captured well-being data

Sobi

Eftrenonacog alfa/Alprolix® - Efmorocog alfa/Elocta®Clinical Study No: Sobi.HAEM89-007

6 Investigational plan

6.1 Overall study design and plan

This is a prospective, low-interventional, single-arm, multicentre study to describe the joint health over an 18-month period of prophylactic treatment with rFVIIIFc or rFIXFc in patients with haemophilia A or haemophilia B in a real-world setting. Approximately 250 patients will be enrolled in the study. Around 80% of the patients are expected to have haemophilia A and around 20% haemophilia B.

Retrospective data from patient medical records will be collected for at least 6 months before enrolment in the study. From enrolment and throughout the study, patients will perform on-site study visits at 6-month intervals. Each patient is expected to actively participate in the study for 18 months (from baseline to end of study [EOS] visit).

Joint health will be assessed with HEAD-US and HJHS scoring. Quality of life and physical activity will be assessed with PROs. Patients will be on prophylactic treatment with rFVIIIFc or rFIXFc according to usual clinical practice and the dosing guide in the respective Summary of Product Characteristics (SmPC). Choice of treatment will not be dictated by the study protocol.

The recruitment period is planned to be approximately 12 months from the timepoint when the first patient is enrolled in the study. Around 60 sites in approximately 11 European countries are expected to participate in the study.

No specific evaluation committees will be utilized for this study, since it is a low-interventional study having no interventions posing more than minimal risk to the patients.

Interim analyses are planned to be performed during the study. The first interim analysis is to be performed once recruitment is completed. The purpose of the first interim analysis is to assess the baseline variability of HEAD-US score results and to share baseline characteristics with the haemophilia community. The second interim analysis is planned to be performed once at least 50% of the patients have completed their 12-month visit and will evaluate the joint health status at that time.

In an optional, exploratory sub-study, data will be collected via the florio HAEMO app. All exploratory endpoints and objectives in the study are related to the exploratory sub-study.

[figure not shown]
The overall study design is described in Figure 1.

Sobi

Eftrenonacog alfa/Alprolix® - Efmorocog alfa/Elocta®

Clinical Study No: Sobi.HAEM89-007

Figure 1 Study Design

6.2 Discussion of study design, including the choice of control groups

This prospective, low-interventional, multicentre study is being conducted to describe the joint health over an 18-month period in patients on prophylactic treatment with rFVIIIFc or rFIXFc with haemophilia A or haemophilia B in a real-world setting. The 18-month follow-up period is considered to be long enough to see changes and/or show medium/long-term stabilization of joint status. Patients treated on demand are not included in the study, as this would lead to a too high variability in the patient population.

Joint outcomes will be described over time and reported in a quantitative/objective manner with HEAD-US and HJHS scores. These assessments are not always fully incorporated in routine clinical practice and are therefore intended to be investigated in the low-interventional setting of this study. Both examinations have been chosen due to their complimentary features – HJHS is a clinical assessment focused on functionality and HEAD-US is a more sensitive US assessment with the ability to detect structural joint damage and synovitis earlier on in the joint deterioration.

This study will not have a control group. The reason for this is that it is not considered needed to be able to evaluate the primary objective of the study.

Patients excluded from participation in this study (section 6.3.2) will have been assessed as not being suitable for the study.

6.2.1 Patient input into design

Representatives from patient organizations in six countries – Czech Republic, France, Germany, Italy, Spain and Sweden, joined Patient Council meetings and provided input on the study design which included objectives and endpoints, PRO scales, visit schedule and study assessments. Their feedback resulted in the decision on the PROs to be used in the study and their format, and also influenced the decision on study duration. The group appreciated a study with focus on both joint health and pain.

Confidential

Page 19 of 56

Version 1.0 Final 15 November 2022

Sobi

Eftrenonacog alfa/Alprolix® - Efmorocog alfa/Elocta®

Clinical Study No: Sobi.HAEM89-007

6.3 Selection of study population

Children from the age of six are allowed to be enrolled in the study. To enrol children in this type of study is considered justified since the study is not posing more than minimal risk to the participating patients and signs of joint damage due to haemophilia are known to develop from an early age. It is judged that children from the age of six are able to comply with study procedures without any major impact on their daily life.

Prospective approval of a protocol deviation to recruitment and enrolment criteria, also known as protocol waiver or exemption, is not permitted.

6.3.1 Inclusion criteria

A patient must fulfill the following criteria in order to be included in the study:

1. Age \geq 6 years
2. Diagnosis of haemophilia A or B
3. Having at least 6 months documented pre-study treatment data regarding treatment prescriptions and bleeding episodes prior to the baseline visit
4. Previous treatment for haemophilia A or B with any marketed recombinant and/or plasma-derived FVIII or FIX concentrate for at least 6 months
5. Start of prophylactic treatment with rFVIIIFc or rFIXFc prior to study enrolment or latest at the baseline visit, in accordance with local regulations
6. Signed and dated informed consent provided by the patient, or the patient's legally authorized representative for patients under the legal age. Assent should be obtained from paediatric patients in accordance with local regulations

6.3.1.1 florio HAEMO sub-study

To be eligible for the florio HAEMO sub-study a patient should have used florio HAEMO (a CE marked medical device used in routine clinical practice) for at least 3 months and must agree to have data collected from the florio HAEMO app by providing a separate informed consent or assent.

6.3.2 Exclusion criteria

The presence of any of the following will exclude a patient from inclusion in the study:

1. Any medical condition which in the opinion of the investigator makes the patient unsuitable for inclusion
2. Prophylactic treatment with non-factor therapy during the 6 months prior to enrolment
3. Presence of factor VIII or FIX inhibitory antibodies (inhibitors) (≥ 0.60 Bethesda Units [BU]/mL) at the latest available inhibitor test
4. Enrolment in a concurrent clinical interventional study, or intake of an Investigational medicinal product, within 3 months prior to inclusion in this study

Sobi

Eftrenonacog alfa/Alprolix® - Efmorocog alfa/Elocta®

Clinical Study No: Sobi.HAEM89-007

5. Foreseeable inability to cooperate with given instructions or study procedures

6.3.3 Withdrawal of patients from study

6.3.3.1 Withdrawal from study

Whenever possible and irrespective of the reason for withdrawal, the patient should be examined as soon as possible. All relevant assessments should be completed, preferably according to the schedule of events (see section 6.5.1.1). The Case report form (CRF) should be completed as far as possible. Date and reason for the study withdrawal should be clearly described in the CRF.

A patient should be withdrawn from the study for any one of the following reasons:

- The patient develops factor VIII or FIX inhibitory antibodies (inhibitor titre ≥ 0.60 BU/mL)
- The patient or his legally authorized representative(s) withdraws consent
- The patient enrolls into an interventional clinical study in which an investigational treatment or approved therapy for investigational use is administered
- The patient enrolls into a low-interventional clinical study where the assessments performed are of such nature that the patient cannot be considered treated per usual routine practice
- The patient discontinues prophylactic treatment with rFVIIIFc or rFIXFc
- The patient is no longer willing to undergo the mandatory US examination

If any Adverse Event (AE) is associated with the withdrawal this should be recorded in the CRF.

If the patient withdraws consent for disclosure of future information (data, samples), the sponsor may retain and continue to use any data collected before such a withdrawal of consent.

Patients will not be withdrawn if they miss a study visit.

If a patient withdraws from the study and more than 3 months since the last study visit have passed, all assessments should be performed to the extent possible. If a patient withdraws from the study less than 3 months since the last visit, PRO collection and HJHS assessment should be performed to the extent possible.

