6.3.4 Replacement of withdrawn patients

Withdrawn patients will not be replaced.

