9.4 Protocol deviations

A protocol deviation is generally an unplanned excursion from the protocol that is not implemented or intended as a systematic change. The investigator is responsible for ensuring the study is conducted in accordance with the procedures and evaluations described in this protocol and must protect the rights, safety, and welfare of patients. The investigator should not implement any deviation from, or changes of, the protocol, unless it is necessary to eliminate an immediate hazard to study patients.

A protocol waiver is a documented prospective approval of a request from an investigator to deviate from the protocol. Protocol waivers are strictly prohibited.

For the purpose of this protocol, deviations requiring notification to CRO are defined as any patients who:

- Entered into the study even though they did not satisfy entry criteria;
- Developed withdrawal criteria during the study and were not withdrawn;

When a deviation from the protocol is identified, the investigator or designee must ensure the CRO is notified. The CRO will follow up with the investigator, as applicable, to assess the deviation and the possible impact to the safety and / or effectiveness of the patient to determine patient continuation in the study.

The investigator and CRO must contact Sobi immediately if a deviation is discovered that significantly affects or has the potential to significantly affect human patient protection or the reliability of study results.

The investigator will also assure that deviations are reported and documented in accordance with IEC and applicable regulatory requirements.

Sobi

Eftrenonacog alfa/Alprolix® - Efmorocog alfa/Elocta®Clinical Study No: Sobi.HAEM89-007

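### A patient who no longer accepts the ultrasound should be withdrawn from the whole study, so later follow-up that needs no ultrasound goes uncollected

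*Combined protocol and SAP*

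**What the plan says.** Section 6.3.3.1 introduces its list with "A patient should be withdrawn from the study for any one of the following reasons". One entry is "The patient is no longer willing to undergo the mandatory US examination". The section offers no option to stop the scan alone and stay in for the rest. It also states "Patients will not be withdrawn if they miss a study visit".

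Section 9.4 names, as a deviation to be notified to the CRO, patients who "Developed withdrawal criteria during the study and were not withdrawn", and it prohibits waivers. Section 6.3.4 adds "Withdrawn patients will not be replaced".

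Other provisions limit the loss. Section 6.3.3.1 asks for an examination at withdrawal whatever the reason. If "more than 3 months since the last study visit have passed, all assessments should be performed to the extent possible"; if "less than 3 months since the last visit, PRO collection and HJHS assessment should be performed to the extent possible". Section 6.5.1.5 repeats this. Even where a patient withdraws consent to future disclosure, "the sponsor may retain and continue to use any data collected before such a withdrawal of consent". The full analysis set in section 8.2 is everyone enrolled. Under section 6.5.12.13, related adverse events are still followed once participation ends, but are not entered in the eCRF.

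**The concern.** The two rules sit oddly together. A patient who misses a visit, scan included, stays in. A patient who attends, reports bleeds, remains on prophylaxis and declines only the scan should leave. The protocol gives no reason beyond calling the examination mandatory.

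What is at stake is follow-up that does not depend on the scan: the bleeding rates, target joints, month-18 HJHS, PROMIS, IPAQ-SF and safety. Once the patient is withdrawn these are no longer collected. The gap arises from the rule rather than from the patient's wish to leave, and the patient is not replaced.

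**Working it through.** **1. Which endpoints need the ultrasound.** This follows from sections 5.1.1, 5.2.1, 6.5.6, 8.2 and 8.3.4. The last column takes a patient withdrawn at month 6.

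| Item | Needs ultrasound? | Effect of withdrawal at month 6 |
|---|---|---|
| Total HEAD-US and its three items | Yes | Earlier scores kept; no later scan possible |
| Bleeding rates | No | Months 6–12 and 12–18 empty; the first 6 months still count, since 3 months of documentation suffice |
| Target joints after baseline | No, derived from reported bleeds | Nothing derivable after month 6 |
| HJHS | No | Exit value requested; month-18 value not obtained |
| PROMIS, IPAQ-SF | No | Exit values requested; month-18 values not obtained |
| Safety events in the eCRF | No | None recorded after the last visit |
| Per-protocol set | Requires completing the study | Patient leaves the set for every endpoint analysed on it |

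**2. Does withdrawal help the primary analysis?** The precision statement in section 8.1 uses SD 13 and n = 250. Half width = 1.96 × SD / √n = 1.96 × 13 / √250 = 1.61, as stated; with n = 200 it is 1.80, also as stated.

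Suppose, pessimistically, that refusers contribute nothing at all to the primary estimate:

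- 2% refuse: n = 245, half width 1.63
- 5% refuse: n = 237.5, half width 1.65
- 10% refuse: n = 225, half width 1.70
- the half width reaches 2 only at n = (1.96 × 13 / 2)² ≈ 162, about 35% loss

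These values are the same whether refusers are withdrawn or kept, because a scan that is refused is missing in both cases. The repeated-measures model in section 8.3.3 can use scores already obtained either way. The only possible difference runs against withdrawal: a retained patient might later accept a scan.

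**3. How much other follow-up is lost.** Planned prospective follow-up is 250 × 18/12 = 375 patient-years. The documents give no refusal rate, so the rates below are assumptions.

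- Per patient refusing at month 6: (18 − 6)/18 = 12/18 = 67% of prospective follow-up.
- 2% at month 6: 250 × 0.02 × 12/12 = 5 patient-years; 5/375 = 1.3%.
- 4% at month 6: 250 × 0.04 × 12/12 = 10 patient-years; 10/375 = 2.7%.
- 10% at month 6: 25 patient-years; 25/375 = 6.7%.
- 2% to 10% at month 12: 250 × 0.02 × 6/12 = 2.5 to 250 × 0.10 × 6/12 = 12.5 patient-years; 0.7% to 3.3%.

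At 2–4%, the month-18 HJHS and PRO values of 5–10 of 250 patients are also not obtained, partly offset by earlier exit values.

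**The case against.** The strongest reply is that the two rules cover different situations. Being no longer willing describes a settled refusal of the assessment that defines the study, while a missed visit is an isolated gap. HEAD-US is the primary endpoint, section 4.2 gives objective joint data as the study's purpose, and a sponsor may prefer not to continue visits and questionnaires for patients who will not have the scan. That is a tenable design preference, so the rules differ in effect but do not formally contradict each other. The documents do not state this reasoning, however, and it does not make the other endpoints depend on the scan.

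Three stronger readings are tempting and not supported:

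- A reader might infer that a refuser's data are discarded. They are not: earlier data are retained, and exit HJHS and PROs are requested. In the month-6 example these exit values would exist, though at the wrong time for the month-18 endpoints.
- A reader might infer that withdrawal is absolute. The list says a patient should be withdrawn, not must be. Section 9.4 still leaves a site little room, since keeping the patient is notifiable and waivers are prohibited.
- A reader might infer that patients who skip several visits are expressly protected. The text speaks of missing a visit, in the singular, and does not address repeated misses. Nor does a missed visit necessarily lose bleeding data: bleeds are recorded by date, and nothing bars entering them later.

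It is also fair that reporting an unapplied withdrawal criterion follows from having the criterion at all. Section 9.4 is not a separate fault; it only makes the rule bite.

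**Conclusion.** The point holds as a low-cost improvement. Under section 6.3.3.1, settled refusal of the scan ends collection of endpoints that do not need it and removes the patient from the per-protocol set, without adding any HEAD-US data. The loss is confined to follow-up after withdrawal and to the month-18 timing of HJHS and PROs.

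The aggregate effect is probably small: 1.3–2.7% of planned follow-up if 2–4% refuse at month 6, and up to 6.7% if 10% do. All of these rest on assumed refusal rates. For an individual refuser at month 6 the loss is two thirds of prospective follow-up. No figure stated in the protocol changes, and the study plans no formal hypothesis test, so no main conclusion is threatened.

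**What to change.** Remove the ultrasound bullet from the withdrawal reasons in section 6.3.3.1 and add a sentence such as: a patient who declines the ultrasound may, with continued consent, remain in the study for all other assessments; HEAD-US is recorded as not done with the reason, and is offered again at each later visit including month 18. State that this is a missed assessment and does not fall under the withdrawal-criterion item of section 9.4. Because section 8.2 does not define a major violation, the SAP should also say whether missing HEAD-US alone excludes a patient from the per-protocol set.

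The cost is one bullet removed and one or two sentences added. The visits are already scheduled, and treatment is unaffected. The one small downside is that patient numbers will differ slightly between the HEAD-US tables and the others.
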